#### **1.4.3. Rationale for Chosen Endpoints**

A continuous monitoring approach to assess the safety and tolerability of the treatment regimen will allow for rapid identification of emergent safety trends on an ongoing basis.

A PK bridging approach was taken, because current knowledge suggests that due to similar disease etiology, the treatment effect of itacitinib in pediatric and adult patients will be similar if similar exposures are achieved. Therefore, PK endpoints are included in this study as primary endpoints in Phase 1, as they will inform the Phase 2 dose and dosing in subsequent cohorts, and secondary endpoints in Phase 2 to further inform dosing by characterizing intrinsic and extrinsic factors of variability in pediatric patients.

The lack of consistency and standardization in the conduct of GVHD clinical studies has been identified as a major obstacle to the progress of clinical studies and the development of new treatments. Recent recommendations of the American Society for Blood and Marrow Transplantation recognize this observation and advocate for clinical studies with well-established endpoints and sample sizes sufficient enough to warrant meaningful statistical interpretation. Using response rate as an example, the timepoint to assess response to therapy should be standardized across studies, because response measurements made too early (eg, less than 2 weeks) might not allow for sufficient time to observe therapeutic benefit, but response measurements made too late (> 6 weeks) may overlook potential benefit (Martin 2008). Consensus has emerged to use Day 28 as a standard response evaluation timepoint in SN-aGVHD treatment studies, because this endpoint has significant prognostic value with longer

term outcomes such as 6-month and 2-year NRM ([MacMillan et al 2010](#), [Saliba et al 2012](#), [Levine et al 2010](#)).

#### 1.4.4. Dose Rationale

In adults with aGVHD who are SN, the starting dose is 200 mg QD. This dose was selected based on data from a clinical study comparing 200 mg QD and 300 mg QD in patients with aGVHD. Thirty aGVHD patients were randomized to 1 of 2 treatment cohorts (200 mg cohort, n = 14; 300 mg cohort, n = 16). This study involved both SR and SN patients. One subject was randomized to the 200 mg cohort but withdrew from the study before starting treatment. The Day 28 ORR in treatment-naive aGVHD subjects in both treatment cohorts was 83.3%; Day 28 ORR was 64.7% (200 mg cohort, 62.5%; 300 mg cohort, 66.7%). Most responses occurred within the first 14 days of treatment, and responses were durable, with a median DOR of 130 days and 136 days in the 200 mg cohort and 300 mg cohort, respectively.

Pharmacokinetics of itacitinib were evaluated using plasma samples collected pre-dose and 1 hour, 2 hours, and 4 to 8 hours postdose on Study Days 1 and 7. Although intersubject variability was found to be high, PK exposure was consistent with historical data, and a large overlap in steady-state exposure was observed between the 200 mg and 300 mg cohorts. These findings contributed to the identification of the 200 mg dose of itacitinib as the recommended phase 2 dose for future GVHD studies ([Schroder et al 2016](#)).

One DLT of Grade 3 thrombocytopenia was reported in 1 subject with pre-existing thrombocytopenia who was randomized to the 300 mg cohort. Adverse events reported in greater than 20% of all subjects included diarrhea, hypokalemia, peripheral edema, hyperglycemia, abdominal pain, hypophosphatemia, fatigue, headache, hypomagnesemia, and sepsis. Thrombocytopenia and platelet count decreases were observed at a total of 20.7% and 24.1% of subjects in both treatment groups, respectively, with a higher proportion of these events occurring in the 300 mg cohort, although a higher incidence of pre-existing thrombocytopenia was also observed in this group. Thrombocytopenia was observed in 14.3% and 26.7% of the subjects in the 200 mg and the 300 mg cohorts, respectively. Platelet count decreases were observed in 7.1% and 40.0% of the subjects in the 200 mg and the 300 mg cohorts, respectively. Adverse events were reflective of the patient population, and there were no safety issues that warranted further action or modification to the study design. With the exception of thrombocytopenia/platelet count decreases, which were more often observed in the 300 mg itacitinib group, no significant differences were observed between the treatment arms with respect to the frequency or severity of AEs.

The addition of itacitinib to corticosteroids did not exacerbate the safety profile of corticosteroids. Moreover, the minimal inhibitory of JAK2 (seen at pharmacologically relevant dose in both preclinical and clinical studies) may reduce the risk of cytopenia, which is a potential additional benefit for this patient population who recently underwent bone marrow transplant and many of whom will enter the study with compromised bone marrow function (55%).

[figure not shown]
To summarize, the following findings led to the selection of a 200 mg dose of itacitinib as the appropriate starting dose for future clinical studies in adult patients with aGVHD:

- The higher incidence of thrombocytopenia in the 300 mg cohort.
- The observation of 1 DLT of Grade 3 thrombocytopenia in the 300 mg cohort, and the absence of DLTs in the 200 mg cohort.
- Similarities in Day 28 ORR between dose cohorts.
- Similarities in PK between dose groups.
- Similarities in Day 28 ORR in standard-risk and high-risk aGVHD between dose cohorts.

In addition, similarities in the discontinuation of corticosteroid use between dose cohorts were observed as well as similar changes in clinical chemistry parameters relevant to the population under study between dose cohorts.

[figure not shown]
The starting dose for each age cohort in children was based on allometric scaling, combined with an age-based maturation function in children younger than 2 years, to predict exposures after oral administration with various doses in pediatric patients with GVHD. A PK bridging approach was used such that starting doses across the age range of 28 days to 18 years were identified that achieved exposures similar to those achieved in adult GVHD patients. The following oral dosing regimens in pediatric patients are recommended: 200 mg QD in children from 12 years and older, 100 mg QD in children from 6 to < 12 years old, 50 mg QD in children from 2 to < 6 years old, 35 mg in children less than 2 weighing more than 8 kg, and 1.4 mg/kg in children weighing 8 kg or less. The median predicted exposure of these doses remains within the approximate interquartile range of the exposures achieved in adult patients with GVHD ([Figure 4](#) and [Figure 5](#)). Additionally, considering observed PK variability in adults and variability in body weights of children of a given age and gender, the predicted range of exposure in children is not expected to significantly exceed that observed in adults ([Figure 4](#) and [Figure 5](#)). Details regarding these dose projections are provided in a separate report (DMB-17.13.2) These dose projections are based on several assumptions regarding variability, the magnitude of the impact of body weight and maturation, and assumed relative bioavailability of the absorption adjustment factors compared with the adult formulation (which was assumed to be 1). The dose will be re-evaluated as data become available regarding the validity of these assumptions. Details regarding dose evaluation based on emerging data from this study are presented in Section [9.6](#).

**Figure 4: Simulated Median and 95% Prediction Interval of Exposures in Children Ages 2 to 5 Years Receiving 50 mg QD, 6 to 11 Years Receiving 100 mg QD, and 12 Years and Older Receiving 200 mg QD Compared With Adults With GVHD**

Clearance = 74.4 L/h, the clearance observed in adults with GVHD receiving 200 mg QD. Variability equal to 200 mg QD dosing in adult added (58% CV).  
Median = solid lines; 95% Prediction Interval = dashed lines; 50 mg QD = squares; 100 mg QD = triangles; 200 mg QD = diamonds.  
Boxplots: data from both doses (200 mg and 300 mg; left) and 200 mg only (right).

**Figure 5: Simulated Median and 95% Prediction Interval of Exposures in Children Weighing  $\leq$  8 kg Receiving 1.4 mg/kg or Children Weighing  $>$  8 kg Receiving 35 mg Compared With Adults With GVHD**

Clearance = 74.4 L/h, the clearance observed in adults with GVHD receiving 200 mg QD. Variability equal to 200 mg QD dosing in adult added (58% CV).

Median = solid lines; 95% Prediction Interval = dashed lines; 1.4 mg/kg QD = circles; 35 mg QD = squares.  
Boxplots: data from both doses (200 mg and 300 mg; left) and 200 mg only (right) from Study INCB 39110-108.  
Small N at 17 kg results in convergence of the 95% PI to the median value.

## 1.5. Potential Risks and Benefits of the Treatment Regimen

Adverse events that have been most frequently reported in at least 10% of adult subjects receiving itacitinib monotherapy include anemia, thrombocytopenia, diarrhea, nausea, fatigue, and upper respiratory tract infection.

As a result of itacitinib-mediated immunomodulation, an increased incidence of infections could possibly occur with itacitinib therapy. Strict medical monitoring is indicated to identify and treat infections in study subjects should they occur.

Because of the potential for myelosuppression, subjects will have hematologic parameters closely monitored during clinical studies. If there are clinically relevant declines in hematology parameters, therapy may be interrupted until resolution or discontinuation. As itacitinib also has the potential to cause WBC margination (ie, a transient decrease in ANC), assessment of

hematology parameters should be performed before study drug administration and at all applicable study visits.

As described previously, murine models of JAK/STAT inhibition using both ruxolitinib and itacitinib have demonstrated a decrease in the expression of CXCR3, reduction of GVHD, preservation of the beneficial GVT effect, and improvement in survival. To the extent that the thrombocytopenia and anemia observed with ruxolitinib reflects the inhibition of JAK2-mediated erythropoiesis and thrombopoiesis, a selective JAK1 inhibitor would likely be associated with a lower incidence of thrombocytopenia and anemia, while still resulting in a significant reduction in the production and the signaling of inflammatory and immune cytokines. It is therefore of interest to evaluate a selective JAK1 inhibitor in this setting given the hematologic complications associated with aGVHD.

In a Phase 1 study in aGVHD subjects (INCB 39110-108), treatment interruptions and stepwise 100 mg dose reductions were used to manage toxicity. In an analysis of the data, efficacy was not affected in subjects who demonstrated Day 28 response and had a dose reduction for any reason. Dose reductions also facilitated platelet recovery in subjects with platelet count decreases receiving treatment, although recovery was also observed in subjects who did not have a dose reduction. Thus, the proposed itacitinib tapering schedule is not expected to negatively affect efficacy in responding subjects, and clinicians are permitted to re-escalate the dose of itacitinib in subjects who initiate a taper but subsequently begin to demonstrate signs or symptoms of GVHD progression.

Observed data from Study INCB 39110-108 demonstrated that there is an approximate 2-fold increase in exposure when itacitinib is coadministered with posaconazole. Given the risk/benefit profile observed in Study INCB 39110-108, no dose adjustment is recommended with coadministration of posaconazole. In a healthy volunteer study, coadministration of itacitinib 200 mg with itraconazole 200 mg QD resulted in a nearly 5-fold increase in exposure of itacitinib. Posaconazole is a less potent CYP3A4 inhibitor than itraconazole based on fold increase in midazolam exposure with coadministration, 6.23 compared with 10.8 ([University of Washington School of Pharmacy 2002](#)), which could explain the difference in exposure change between coadministration of itacitinib with posaconazole or itraconazole. However, taking into consideration the result of the healthy volunteer drug interaction study with itraconazole and given the lack of information regarding the risk/benefit profile in patients receiving strong CYP3A4 inhibitors more potent than posaconazole, subjects taking the following potent CYP3A4 inhibitors should have a dose reduction of itacitinib to half of the initial dose (eg, from 200 mg to 100 mg QD): itraconazole, voriconazole, mibefradil, and clarithromycin. No dose adjustment is recommended for concomitant administration of other CYP3A4 inhibitors.

Because overall pathophysiology, clinical manifestation, patient management, treatment and prognosis are comparable in both adult and pediatric populations (see Sections [1.1](#) and [1.4](#)), itacitinib is expected to act in the same way in adult and pediatric aGVHD population. Thus, a comparable benefit without a significantly increased safety risk is expected in the pediatric population.

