#### **5.6.3. Criteria and Procedures for Dose Interruptions and Modifications of Itacitinib**

If the drugs need to be interrupted due to toxicity, subjects should be evaluated on a weekly basis until resolution/improvement of the AE. Subjects may resume treatment if no medical condition or other circumstance exists that, in the opinion of the investigator, would make the subject unsuitable for further participation in the study. Treatment with itacitinib may be delayed up to 14 days to allow for resolution of toxicity. The investigator should contact the sponsor medical monitor to discuss cases where treatment has been delayed for more than 14 days before restarting treatment.

Because subjects may enter the study with compromised bone marrow function, these dose reductions are provided as guidelines (see [Table 3](#) and [Table 4](#)); individual decisions regarding dose reduction should be made using clinical judgment and an individual benefit/risk assessment, taking into account relatedness of the AE to the study drug and the subject's underlying condition. Adverse events that have a clear alternative explanation or transient ( $\leq 72$  hours) abnormal laboratory values without associated clinically significant signs or symptoms may be exempt from dose-reduction rules.

The starting dose in each cohort may be reduced based on toxicity (ie, approximately 50% of the initial dose in each cohort). The dose might also be modified based on PK data. Subjects who

are unable to tolerate itacitinib at the reduced dose (50% decrease of the initial dose in each cohort) should be withdrawn from study treatment. The sponsor's medical monitor may be consulted for advice.

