**Table 3: Guidelines for Interruption and Restarting of Itacitinib**

ADVERSE EVENT	ACTION TAKEN
Chemistry	

 
AST and/or ALT <math>> 3.0 \times \text{ULN}</math>
 
	
 
Interrupt for up to 14 days until the toxicity has resolved to <math>\leq</math> Grade 1. Exceptions require sponsor approval.
 
Restart at previous dose. If assessed as related to itacitinib, restart at next lower dose and monitor as clinically indicated.
 

 
Total bilirubin elevations that occur in the presence of GVHD response that cannot be attributed to new liver GVHD or concomitant therapy.
 
	
Total bilirubin <math>3.0\text{-}5.0 \times \text{ULN}</math>:
 
 
Reduce dose by 1 level and repeat assessment within 7 days. If elevation persists: 
 
Interrupt until bilirubin <math>\leq 1.5 \times \text{ULN}</math>.
 
Monitor LFTs weekly or more frequently as appropriate.
 
Resume previous dose if resolved in 14 days; if <math>> 14</math> days, maintain reduced dose.
 
 
 
 
Total bilirubin <math>> 5.0\text{-}10.0 \times \text{ULN}</math>:
 
 
Interrupt and repeat assessment within 7 days. If elevation persists: 
 
Keep interruption until bilirubin <math>\leq 1.5 \times \text{ULN}</math>.
 
Monitor LFTs weekly or more frequently as appropriate.
 
Resume previous dose if resolved in 14 days; if <math>> 14</math> days, resume at reduced dose.
 
 
 
 
Total bilirubin <math>> 10.0 \times \text{ULN}</math>:
 
 
Interrupt and repeat assessment within 7 days. If elevation persists: 
 
Keep interruption until bilirubin <math>\leq 1.5 \times \text{ULN}</math>.
 
Monitor LFTs weekly or more frequently as appropriate.
 
Resume at reduced dose if resolved in 14 days; if <math>> 14</math> days, discontinue treatment and monitor as appropriate.
 
 
 

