**Table 4: Potential Dose Reduction and Increase Levels for Itacitinib**

Current Dose	First Dose Reduction	Second Dose Reduction
Initial dose for each cohort disclosed in Section 5.2.1	50%	Discontinue

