## 5.7.5. Restricted Medications

The following medications have restrictions on use during the treatment period of the study:

- Aspirin.
- Coadministration with the following potent CYP3A inhibitors: itraconazole, voriconazole, mibepradil, and clarithromycin. If the subject's medical condition requires treatment with any of these drugs, dose reduction of itacitinib is recommended as follows (see rationale in Section 1.5):
  - In children 12 years of age and older, doses should be reduced to 100 mg QD.
  - In children 6 to < 11 years old, doses should be reduced to 50 mg QD.
  - In children 2 to < 6 years old, doses should be reduced to 25 mg QD.
  - In children > 8 kg but < 2 years old, doses should be reduced to 17.5 mg QD.
  - In children  $\leq$  8 kg but  $\geq$  28 days old, doses should be reduced to 0.7 mg/kg QD.

The coadministration with those medications should be avoided during the 28-day surveillance period in subjects enrolled in Part 1 of the study. The sponsor's medical monitor may be consulted for advice when using these agents. No dose adjustment is recommended for concomitant administration of other CYP3A4 inhibitors.

- Coadministration with potent CYP3A4 inducers.
- If concomitant administration of an anticoagulant/antiplatelet medication is indicated, then caution and enhanced monitoring is required. History of thrombocytopenia should be a factor in the choice of anticoagulant and dose.

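### The only itacitinib dose named for use with a listed potent CYP3A inhibitor equals the single toxicity-reduced dose, so a child kept at 50% for related toxicity gets no further written reduction

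*Combined protocol and SAP*

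**What the plan says.** **Interaction rule.** Section 1.5 states that "subjects taking the following potent CYP3A4 inhibitors should have a dose reduction of itacitinib to half of the initial dose". The drugs are itraconazole, voriconazole, mibefradil and clarithromycin; Administrative Change 1 adds ketoconazole on the same basis. Section 5.7.5 converts the rule into fixed amounts by age or weight. The first is "In children 12 years of age and older, doses should be reduced to 100 mg QD"; the others are 50 mg, 25 mg, 17.5 mg and 0.7 mg/kg. That section asks sites to avoid these drugs during the 28-day surveillance period of Part 1, and says the medical monitor may be consulted.

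**Reason for the rule.** Section 1.5 reports that "coadministration of itacitinib 200 mg with itraconazole 200 mg QD resulted in a nearly 5-fold increase in exposure of itacitinib". For posaconazole, "there is an approximate 2-fold increase in exposure when itacitinib is coadministered with posaconazole", and no adjustment is recommended. The stricter rule for the listed drugs is adopted "given the lack of information regarding the risk/benefit profile in patients receiving strong CYP3A4 inhibitors more potent than posaconazole".

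**Toxicity rule.** Section 5.6.3 says: "The starting dose in each cohort may be reduced based on toxicity (ie, approximately 50% of the initial dose in each cohort". Table 4 has one row, starting from "Initial dose for each cohort disclosed in Section 5.2.1", with a first reduction of 50% and then discontinuation. For AST/ALT elevation, Table 3 says: "If assessed as related to itacitinib, restart at next lower dose and monitor as clinically indicated". Its row for clinically significant Grade 3 toxicity that supportive care cannot manage gives the same instruction. Neither row names a return to the earlier dose. The rows for related neutropenia and related thrombocytopenia do allow a return after recovery.

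No section says what to do when a child already at the 50% dose needs a listed inhibitor.

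**The concern.** The interaction reduction exists to offset a rise in exposure. Because it is anchored to the initial dose, it has nothing left to act on once the dose has been halved for another reason. An adolescent already at 100 mg cannot be reduced to 100 mg, and a site reading section 5.7.5 could reasonably conclude that the child is already at the right dose.

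The children concerned are those with toxicity judged related to itacitinib at full dose. If a new co-medication takes their exposure back above that level, the toxicity may return. Table 4 then offers only discontinuation, so a child could lose study treatment because of an uncorrected interaction.

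The sequence is plausible. Anti-infective treatment is permitted and prophylaxis is described as routine (section 5.4). The request to avoid the listed drugs does not extend past the surveillance period or into Phase 2.

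**Working it through.** **Step 1: compare the two doses.** Initial doses are from section 5.2.1, interaction doses from section 5.7.5. Toxicity dose = 0.5 × initial dose (section 5.6.3, Table 4).

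| Cohort | Initial | Toxicity dose | Interaction dose | Further cut |
|---|---|---|---|---|
| 1 | 200 mg | 100 mg | 100 mg | 0% |
| 2 | 100 mg | 50 mg | 50 mg | 0% |
| 3 | 50 mg | 25 mg | 25 mg | 0% |
| 4 | 35 mg | 17.5 mg | 17.5 mg | 0% |
| 5 | 1.4 mg/kg | 0.7 mg/kg | 0.7 mg/kg | 0% |

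The protocol's half-of-initial figures are reproduced, and they equal the toxicity dose in every cohort. Section 5.7.5 lists its second group as 6 to under 11 years, while Cohort 2 runs to under 12. For 11-year-olds the general rule in section 1.5 still gives 0.5 × 100 = 50 mg.

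**Step 2: relative exposure.** Let 1.0 be exposure at the full cohort dose without an inhibitor, and f the fold increase with the inhibitor. Assuming dose proportionality, relative exposure = dose fraction × f.

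- Full-dose child under the rule: 1.0 before, 0.5f after (a rise of f/2).
- Child at 50% under the rule: 0.5 before, 0.5f after (a rise of f). This passes 1.0 when f > 2.
- Child at 50%, if the current dose were halved: 0.5 before, 0.25f after. This falls below 0.5 only when f < 2.

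| f | Source | Child at 50%, written rule | Child at 50%, half of current dose |
|---|---|---|---|
| 2 | assumed for a listed drug | 1.0 | 0.5 |
| 3 | assumed | 1.5 | 0.75 |
| 4 | assumed | 2.0 | 1.0 |
| 5 | itraconazole, section 1.5 | 2.5 | 1.25 |

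With itraconazole the child at 50% goes from 0.5 to about 2.5, a 5-fold rise. A full-dose child goes from 1.0 to about 2.5, a 2.5-fold rise. The end level is the same; only the second child received an offsetting reduction. The documents give no itacitinib figure for voriconazole, mibefradil, clarithromycin or ketoconazole, so 2 to 4 is an assumed range for these.

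**Step 3: who is affected.** Mainly children restarted at the lower dose after related AST/ALT elevation or other related Grade 3 toxicity, because Table 3 names no return for them. Children reduced for cytopenias suspected as unrelated, and children already back at full dose, are outside the point. Children with related cytopenias are inside it only until they return to full dose.

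**The case against.** The strongest reply is that the text recommends a dose and does not set a floor. Sections 1.5 and 5.7.5 describe a child coming down from full dose and are silent on one already at half. Section 5.6.1 allows individual modification, section 5.6.3 treats the reductions as guidelines subject to individual benefit/risk judgment, and section 5.7.5 offers medical-monitor advice. This stands: a reader might infer that the protocol forbids a lower dose, and it does not. But none of these provisions names a dose or makes consultation mandatory, while the one number on the page points to no change.

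Second, the sponsor already accepts similar exposure in other children: about 2.0 times at full dose with posaconazole (1.0 × 2), and about 2.5 times for any child on itraconazole at the rule dose. So the end level is not peculiar to this group. What is peculiar is that these children had related toxicity at 1.0; nothing in section 1.5 shows that the accepted levels were considered for them.

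Third, the group is narrow. The toxicity seen more often at the higher adult dose was thrombocytopenia (section 1.4.4), for which Table 3 allows return to the previous dose. Monitoring is also not thin early on: chemistry and hematology are weekly to Day 56, and unscheduled visits are allowed. After Day 56, routine visits are 28 days apart. These points limit the weight of the finding; they do not close the gap.

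Fourth, the multipliers are soft. Section 1.4.2 reports high intersubject variability and a large overlap in exposure between 200 mg and 300 mg, and the 5-fold figure comes from healthy volunteers. This is accepted and stated as an assumption.

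**Conclusion.** The point holds as an individual safety gap in a narrow group. The interaction dose and the toxicity-reduced dose are the same in all five cohorts, the sequence is not addressed, and following the written rule leaves a child with related toxicity uncorrected for the interaction. The size is about 0.5 to about 2.5 times full-dose exposure with itraconazole, and 1.0 to 2.0 times for the other listed drugs at an assumed 2- to 4-fold. These figures rest on dose proportionality and on carrying the healthy-volunteer figure over to children.

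Two stronger readings are not supported. One is that every child at the 50% dose is exposed to the gap; Table 3 excludes many, and the number left is unknown and probably small. The other is that the gap affects the Day 28 response rate; nothing in the documents supports that, and it is not claimed. The point is a cheap improvement to the dosing text, with no bearing on the design or the primary analysis.

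**What to change.** Administrative Change 1 already marks sections 1.5 and 5.7.5 for revision to add ketoconazole. In that amendment, state that for a subject already at a reduced dose for itacitinib-related toxicity:

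- the half-of-initial dose does not count as an interaction adjustment;
- a non-listed agent is preferred;
- if a listed inhibitor is unavoidable, the medical monitor must be consulted before it is started, to agree a further reduction or a temporary hold of itacitinib, with closer laboratory monitoring as clinically indicated.

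A non-listed agent is not always neutral: posaconazole at the 50% dose still gives about 0.5 × 2 = 1.0 times full-dose exposure.

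Half of the current dose can be offered as an example where a formulation allows, but should not be mandated. It would be 50 mg in Cohort 1 and 25 mg in Cohort 2, both multiples of the 25 mg tablet, although section 5.2.1 assigns that tablet only to Cohort 3. In Cohort 3 it would be 12.5 mg, less than one such tablet. In Cohorts 4 and 5 it depends on formulations still in development. A 25% level also lies below anything in Table 4, so the added text should say that it is an interaction adjustment and not a second toxicity reduction.

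The cost is one or two sentences in each section and one extra consultation per affected child, with no added scheduled visits or subjects. The downside is lower dosing or a short hold in a few children, with some risk to GVHD control.
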